12.0 DISCIPLINE REVIEW

There will be no discipline review for this study.

13.0 REGISTRATION GUIDELINES

- 13.1 Patients must be registered prior to initiation of treatment
- 13.2 For either method of registration, the individual registering the patient must have completed the appropriate Registration Form.

Patients will not be registered if the IRB approval date expired.

14.0 ETHICAL AND REGULATORY CONSIDERATIONS

The following will be observed to comply with Food and Drug Administration regulations for the conduct and monitoring of clinical investigations; they also represent sound research practice:

Informed Consent

The principles of informed consent are described by Federal Regulatory Guidelines (Federal Register Vol. 46, No. 17, January 27, 1981, part 50) and the Office for Protection from Research Risks Reports: Protection of Human Subjects (Code of Federal Regulations 45 CFR 46). They must be followed to comply with FDA regulations for the conduct and monitoring of clinical investigations.

Institutional Review

This study must be approved by an appropriate institutional review committee as defined by Federal Regulatory Guidelines (Ref. Federal Register Vol. 46, No. 17, January 27, 1981, part 56) and the Office for Protection from Research Risks Reports: Protection of Human Subjects (Code of Federal Regulations 45 CFR 46).

14.1 Ethics review

The investigator must submit written approval to AstraZeneca before he or she can enroll any subject into the study.

If any modifications are made to the protocol or informed consent documents, the new versions will be submitted to AstraZeneca for approval.

14.2 Audits and inspections

Authorized representative of AstraZeneca, a regulatory authority, and Independent Ethics Committee (IEC) or an Institutional Review Board (IRB) may visit the centre to perform audits or inspections, including source data verification. The purpose of an AstraZeneca audit or inspection is to systematically and independently examine all study-related activities and documents to determine whether these activities were conducted, and data were recorded, analyzed and accurately reported according to the protocol, Good Clinical Practice (GCP), guidelines of the International Conference on Harmonization (ICH), and any applicable regulatory requirements. The investigator should contact AstraZeneca immediately if contacted by a regulatory agency about an inspection at his or her centre.

14.3 Subject data protection

In accordance with the Health Information Portability and Accountability Act (HIPAA), the Written Informed Consent Form must include language that informs the subject that authorized representatives at AstraZeneca will have access to subject's medical information that includes all hospital records relevant to the study, including subject's medical history for research purposes.

15.0 ADVERSE EVENT REPORTING

- 15.1 An **adverse event** is defined as any untoward medical occurrence that occurs from the first dose of study medication until 30 days after the final dose, regardless of whether it is considered related to a medication.

In addition, any known untoward event that occurs subsequent to the adverse event reporting period that the investigator assesses as possibly related to the investigational medication should also be considered an adverse event.

- 15.2 A **preexisting condition** should **not** be reported as an adverse event unless the condition worsens or episodes increase in frequency during the adverse event reporting period.
- 15.3 Symptoms of the targeted cancer should not be reported as adverse events.
- 15.4 A **serious** adverse event is one that is fatal or life-threatening (i.e., results in an immediate risk of death), is permanently or substantially disabling, requires or prolongs hospitalization (only if related to an unexpected complication), or is a congenital anomaly, new cancer or medication overdose. This category also includes any other event the investigator judges to be serious or which would suggest a significant hazard, contraindication, side effect or precaution.
- 15.5 An **unexpected** event is one that is **not** listed as a known toxicity of the investigational drug in the protocol, the consent form, the package insert, or the investigator brochure.
- 15.6 **Serious, unexpected, drug-related** adverse events must be reported to the FDA and to IRB within 10 working days (report deaths within 3 days to the FDA). Please report these events to the FDA on the **MEDWATCH form** and ensure "causality" is assigned.

A cover page should accompany the Medwatch form indicating the following:

- Arimidex Investigator Sponsored Study (ISS)
- The investigator IND number assigned by the FDA
- The investigator's name and address
- The trial name and AstraZeneca Reference number

Send by way of fax to: [contact], Attention Arimidex ISS Safety Representative

If a non-serious AE becomes serious, this and other relevant follow-up information must also be provided to AstraZeneca and the FDA.

10.6.1 Address for submitting **MEDWATCH forms** to the **FDA**:

MEDWATCH
[name]
[name]
FAX #: [name]

MASTER FORMS SET

This section includes copies of all data forms which must be completed for this study. These include:

- a. Registration Form (Form #1)
- b. **DCIS** and Early Invasive Breast Cancer Prestudy Form (Form #2)
- c. Baseline Tumor Assessment Form (Form #3)
- h. Treatment and Toxicity Form
- i. Follow-Up Tumor Assessment Form (Form #4)
- l. Follow-Up Form (Form #5)
- m. Off Treatment Notice (Form #6)
- n. Notice of Death (Form #7)
- o. Specimen submission form

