Angiogenesis plays a fundamental role in tumor growth and metastasis. Investigations by Teruyama et al. and Mastuyugin et al. have established a relationship between VEGF expression and p450 aromatase activity (Teruyama, 2001; Mastuyugin, 2002). We have previously shown that dynamic contrast enhanced MRI in conjunction with compartmental modeling may be used to assess the angiogenic status of tumors while enabling the study of both breasts (Su, 2002). Additionally, image based measurement techniques do not suffer from the errors due to tissue heterogeneity and use of limited spatial sampling imposed in methods such as histology. Furthermore, MRI based parameters that describe breast physiology have been found to correlate well with immunohistochemically measured angiogenesis markers (Su, 1995; Su, 1994; Su, 1996). *Thus, dynamic contrast enhanced MRI will be used as a secondary surrogate marker in the proposed study.*

Methodology to test the hypothesis: Core biopsies will be obtained from patients whose mammographic findings are suspicious for DCIS. Patient will undergo MRI study prior the biopsy. At the time of biopsy, a portion of the tissue retrieved will be sent in formalin for histopathological examination for Ki-67, ER, PR and angiogenesis markers evaluation.

1 mg of anastrozole administered orally daily for 4 weeks after the diagnosis of DCIS/invasive breast cancer. The reason for using a 4-week regimen is that this is the average time between diagnostic biopsy and definitive lumpectomy or mastectomy.

Patients will undergo MRI at baseline before therapy and then again after anastrozole treatment that will be followed immediately by definitive surgical procedure, i.e. lumpectomy or mastectomy. Lumpectomy/mastectomy specimen will be again evaluated for the level of tumor

Ki-67 decline and the level of angiogenesis markers. The specimen will be subjected to the routine histopathological, and ER and PR evaluation. Histopathological changes pre and post anastrozole will be evaluated in an exploratory analysis.

Detailed Methodology

1. **Quantification of Ki-67 as a Primary Marker to Monitor Response to Chemoprevention by Aromatase Inhibitor Anastrozole**

Measurement of Ki-67 Levels.

[figure not shown]
Measurement of **Ki67** will be performed with the MIB1 mouse monoclonal antibody. To ensure acceptable precision, quantitation of Ki67 will involve the counting of 1000 cells.

Other Tissue Biomarkers.

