ER expression will be demonstrated with the DAKO 1D5 mouse monoclonal and PgR with the Novocastra antibody NCL-PgR clone 1A6 For all other analytes, 10 high-powered fields (chosen randomly) will be assessed. ER and PgR will be reported as percentage of positively stained cells.

2. **Dynamic Contrast Enhanced MRI as a Secondary Marker to Quantify Chemoprevention by Anastrozole**

We have investigated the relationship between endoglin (CD105), a marker selectively associated with neo-vascular endothelium, and vascular volume density in early breast cancer. The patients had a preoperative contrast enhanced dynamic MRI and the tissue blocks obtained at surgery were immunohistochemically (IHC) stained for CD105. The dynamic contrast enhanced MRI images were then analyzed by using the compartmental modeling technique as described by us previously to quantify vascular density VB (Su, 1995; Su, 1994; Su, 1998; Su, 1999). The result shown in the next figure summarizes our finding that shows a strong correlation between vascular density (VB) and CD105 score suggesting that the MRI technique to be used in the current investigation provides a measure of tumor angiogenesis in breast cancer.

In another study, Gilles et al. performed preoperative contrast material-enhanced subtraction

dynamic MR imaging in thirty-six women with DCIS. Concomitant early contrast enhancement in the breast parenchyma with normal vessels was considered a positive finding. The size and shape of early enhancement were correlated with the size and density packing of ducts involved by DCIS. Their results indicate that early contrast enhancement was demonstrated in 34 patients with DCIS but not in two patients with comedo-type DCIS. Tumor angiogenesis was demonstrated in the stroma. The size and morphology of contrast-enhanced lesions significantly correlated with the size ($P = .0085$) and density packing of ducts involved by DCIS ($P = .012$). They conclude that enhancement on dynamic MR images of DCIS may be due to the presence of tumor angiogenesis in the stroma (Gilles, 1995).

MRI study that is described below will be repeated twice, once before the therapy at baseline and once after the therapy.

2.a Imaging Technique:

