An IV line will be set up by placing an indwelling cannula in an antecubital vein before patient is placed into the scanner. The patient will then be placed in the prone position with both breasts hanging in a double breast coil. The following image sequences will be performed.

First a 3D slab covering the entire area of interest will be selected for shimming. The study protocol consists of the following pulse sequences:

T1-weighted spin echo pulse sequence. TR= 928 ms, TE=14 ms, matrix size= 256x256, 32 slice with 4 mm thickness, no gap. The scan time is 3 min 07 s.

Fat Sat T2-weighted pulse sequence. TR= 5930 ms, TE=90 ms, matrix size= 256x252, 32 slice with 4 mm thickness, no gap. The scan time is 3 min 39 s.

3D Turbo Flash pulse sequence for sagittal dynamic imaging. TR= 10 ms, TE=3.0 ms, flip angle = 20-degrees, 24 slices with 5 mm thickness. The scan time is 31.8 s per acquisition. Repeat the sequence 16 times for dynamic acquisition, 4 pre-contrast, and 12 post-contrast. The contrast agent (Magnevist[®], 0.1 mmol/kg) will be calculated based on patient's body weight. The injection starts after 4 pre-contrast acquisitions have been completed, and the total injection time will be fixed at 15 sec, i.e. all contrast agents will be administered at constant rate and finish in exactly 15 sec.

For ease of comparison of the images acquired using different pulse sequences, the number of slices, thickness, and location in all 3 pulse sequences are kept the same.

2.b Image Analysis:

Based on the Gd-DTPA enhanced images at 3 minutes after the injection, the tumor regions will be manually outlined slice by slice. Then the enhancement time course of Gd-DTPA from the tumor ROI in each imaging slice will be obtained. For each tumor a mean enhancement time course will be calculated. Then the data will be analyzed following the procedure described below to generate the pixel population distribution curves of each vascular volume parameter (VB). The enhancement time course of Gd-DTPA will be analyzed with the pharmacokinetic model to derive the parameters for vascular volume (VB) and permeability (K₂) information. In each tumor the analysis will be performed on a pixel-by-pixel basis. After the analyses are completed, the derived parameters from all pixels in an imaging slice will be reconstructed into the parameter maps. From all pixels in each tumor, the pixel population distribution curves of

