7.0 TREATMENT PLAN

- 7.1. Patients entered into this trial will be treated with the following regimen.
 - a. Anastrozole 1 mg by mouth for 2 - 4 weeks. The study doctor or a member of the study team will document the exact start time of treatment.
- 7.2 Good Medical Practice

The following pre-study tests should be obtained within 28 days prior to beginning treatment in accordance with good medical practice. Results of these tests do not determine eligibility and minor deviations would be acceptable if they do not impact on patient safety in the clinical judgement of the treating physician. The Study Coordinator must be contacted if there are significant deviations in the values of these tests.

WBC \geq 2,000/ μ l, ANC $>$ 1,000/ mm^3 and platelets $>$ 100,000/ mm^3 .

No serious illness or condition that would compromise ability to comply with protocol treatment and follow up.

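### The adverse event window opens at the first dose, so no routine record is required of events arising between the study's baseline contrast MRI and dosing

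*Combined protocol and SAP*

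**What the plan says.** **Window.** Section 15.1 counts "any untoward medical occurrence that occurs from the first dose of study medication until 30 days after the final dose", whatever the suspected cause. Its only extension runs forward: "any known untoward event that occurs subsequent to the adverse event reporting period that the investigator assesses as possibly related to the investigational medication". Section 15.2 leaves out preexisting conditions unless they worsen or become more frequent within the window.

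**Imaging.** Section 2.0 (Methodology to test the hypothesis) states: "Patient will undergo MRI study prior the biopsy". Under Detailed Methodology, item 2, the MRI "will be repeated twice, once before the therapy at baseline and once after the therapy". Section 2.a describes an invasive procedure: "An IV line will be set up by placing an indwelling cannula in an antecubital vein before patient is placed into the scanner", and "The contrast agent (Magnevist[®], 0.1 mmol/kg) will be calculated based on patient's body weight".

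**Dosing.** Section 2.0 has anastrozole "administered orally daily for 4 weeks after the diagnosis of DCIS/invasive breast cancer". Section 7.1 has "Anastrozole 1 mg by mouth for 2 - 4 weeks".

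**Eligibility.** Section 5.1 starts from mammographic suspicion. Section 5.2 requires confirmation on core biopsy before final registration, and 5.6 requires ER or PR positivity. The Section 9.0 table takes both results from the core biopsy.

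**Other safety text.** Section 8.1 puts acute morbidity of hormonal therapy, during therapy, on a toxicity form. Section 8.2 sends unexpected or fatal toxicities to the Study Coordinator and gives no start date. Section 15.6 sends serious, unexpected, drug-related events to the FDA and IRB, and 15.5 defines unexpectedness by the investigational drug.

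**The concern.** The contrast MRI is not routine care that happens to be recorded. Section 2.0 makes it a secondary surrogate marker, and Specific Aim 3 depends on it. Each scan exposes a woman to a cannula and a contrast injection because of the study.

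The 15.1 definition does not depend on relatedness, so it would capture a reaction to that injection if it occurred inside the window. The second scan is inside and the first is not. The only difference is the date on which the window opens.

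At stake is the completeness of the safety record: what is written down about one of the two study contrast exposures, and about women who had the scan and were never treated.

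**Working it through.** The plan gives no figure for this point, so there is nothing to reproduce. The check is one of sequence, followed by simple counts.

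**1. Order of events.** Contrast MRI, then core biopsy, then diagnosis and receptor status, then final registration, then first dose (Section 2.0 with 5.2, 5.6 and the 9.0 table). Some passages place the first MRI only at baseline or before therapy. On those too it precedes the first dose.

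**2. Length of the window.** With dosing of 2 to 4 weeks (7.1), the window runs from the first dose for
- 14 + 30 = 44 days, up to
- 28 + 30 = 58 days,

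with 0 days before the first dose. The 4 weeks in Section 2.0 and the 2 to 4 weeks in 7.1 need to be reconciled, but the difference moves only the closing date.

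**3. Where each scan falls.** The baseline MRI is outside. Section 2.0 places the second MRI after treatment and immediately before surgery, which is inside. Section 10.3 puts it 4 weeks after anastrozole. Even if that means 28 days after the last dose, 28 < 30, so it is still inside.

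**4. Treated women.** Planned accrual is 42 (Section 11.0). If all are dosed and scanned twice:
- contrast MRIs: 42 × 2 = 84
- before the window: 42 × 1 = 42
- share: 42/84 = 50%

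**5. Women imaged but never dosed.** The plan does not state the fraction f of imaged women who are never dosed. The values below are assumptions that show the range, with 42 women treated. Imaged = 42/(1 − f); never dosed = imaged − 42; share of contrast MRIs outside the window = imaged/(imaged + 42).

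| f (assumed) | Imaged | Never dosed | Contrast MRIs outside window |
|---|---|---|---|
| 10% | 46.7 | 4.7 | 53% |
| 20% | 52.5 | 10.5 | 56% |
| 30% | 60.0 | 18.0 | 59% |
| 50% | 84.0 | 42.0 | 67% |

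**6. Whether other text closes the gap.**
- 8.1 is limited to hormonal therapy and to the time on therapy.
- 15.4 describes a serious adverse event as a kind of adverse event, so it takes over the 15.1 opening date.
- 15.6 requires drug-relatedness.
- The Master Forms Set has a treatment and toxicity form but no event form for the period before treatment.
- 8.2 is the only text without a start date. It sits in the section on treatment toxicity, names no form, and does not reach expected, non-fatal reactions.

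**The case against.** **A drug-anchored window is coherent.** Section 15 is written for a study of anastrozole. The term *study medication* is not defined, but Sections 3.0, 7.1 and 15.5-15.6 point to anastrozole. That explains the rule. It does not explain why the same scan is covered after treatment and not before.

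**Reactions at the first scan are not all lost.** A reader might infer that 15.1 excludes every harm of the baseline MRI. It does not. A delayed event that first arises after the first dose counts whatever its cause, and a pre-dose condition that worsens in the window counts under 15.2. What is lost is an event that arises before dosing and does not worsen later.

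**Undosed women are not wholly without reporting.** A reader might also infer that they have no safety record at all. Read broadly, 8.2 could bring an unexpected or fatal reaction to the Study Coordinator, and Section 11.0 gives the Study Committee a general duty to monitor toxicity. In addition, 8.1 lists injection site reaction although anastrozole is oral, which leaves it unclear whether intravenous events were meant to be captured. The supportable statement is narrower: 15.1 and 8.1 require no routine record before the first dose.

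**The undosed group is inferred.** The plan never describes it. It follows from the MRI-before-biopsy sentence in Section 2.0 together with 5.2 and 5.6. Other passages say only before therapy, and the point of consent to the MRI is not visible in the text available. This stands as a limit on that part of the point. The pre-dose gap in treated women does not depend on it.

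**Changing 15.1 alone would not be enough.** This also stands. A wider window would sit badly with the scope of 8.1, and 15.5-15.6 would still forward only drug-related events, even for a reaction at the second scan.

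**Conclusion.** The point holds as a gap in safety ascertainment created by a stated rule. Followed as written, 15.1 and 8.1 require no record of events that arise between the baseline contrast MRI and the first dose and do not worsen later.

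One of two planned contrast MRIs per treated woman falls outside the window: 42 of 84, if all 42 are dosed and complete both scans. Women imaged and then found ineligible have no window, if the MRI precedes the biopsy as Section 2.0 says. Their number is unknown, and the 5 to 42 shown above rests only on assumed fractions of 10% to 50%.

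A reader might take 42 of 84 to mean that half of the contrast harms go uncounted. The documents do not support that. The figure counts exposures, no contrast reaction rate is given, and the number of missed events could be very small. The Ki-67 analysis, its alpha, its power and the sample size are untouched.

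The change is worth making because it is cheap and improves the safety record, not because any efficacy conclusion depends on it.

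**What to change.** - **15.1:** open the window at the first study-specific procedure after consent, which is the baseline contrast MRI. State that it covers women who are imaged but never dosed, and say when it closes for them.
- **8.1 and its toxicity form:** extend the scope so that events related to study procedures or contrast are recorded, including before therapy. State what the injection site reaction entry refers to.
- **15.5-15.6:** define unexpectedness, relatedness and reporting for study procedures and contrast as well as for anastrozole.
- **8.2:** state whether it applies before the first dose.

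The cost is a short amendment across these sections, a revision of the toxicity form, somewhat more event recording, and brief tracking of women who are imaged but not registered. No sample size or power figure changes. Both planned contrast MRIs per treated woman would then fall inside the window instead of one.

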Human Toxicity: Hot flashes (26.5%) are the most commonly reported adverse reaction to anastrozole during first-line therapy for breast cancer. In patients receiving anastrozole for progressive breast cancer, hot flashes occurred in 12.6% of patients. Vaginal irritation (i.e., dryness) and vaginal bleeding have also been reported with anastrozole. Vaginal bleeding occurs primarily during the first few weeks after changing from existing hormonal therapy to treatment with anastrozole. If bleeding persists, further evaluation should be considered. Tumor flare with associated bone pain has been reported during first-line anastrozole therapy for breast cancer.

GI adverse reactions occurred in up to one-third of patients receiving anastrozole. These reactions included, anorexia, constipation, abdominal pain, diarrhea, nausea/vomiting, and xerostomia (dry mouth). Weight gain has been reported in 2% of patients taking anastrozole, but occurs less frequently than with megestrol. Elevated hepatic enzymes, primarily serum gamma glutamyl transferase (GGT), have been observed in patients with liver metastases receiving anastrozole or megestrol. These changes were likely due to the progression of liver disease in these patients, but other contributing factors cannot be ruled out. Nervous system adverse reactions to anastrozole include anxiety, confusion, depression, dizziness, headache, hypertonia, insomnia, and paresthesias. Thromboembolism has been reported in patients treated with anastrozole (3.5%). The incidence of thrombosis is less than that reported with tamoxifen (6.5%) or megestrol (4.7%) during clinical trials. Specific cases included angina, cerebrovascular accident, cerebral ischemia, cerebral infarct, myocardial infarction, myocardial ischemia, pulmonary embolism, retinal vein thrombosis, and thrombophlebitis.

Other reported adverse events to anastrozole regardless of causality are arthralgia, asthenia, back pain, chest pain (unspecified), diaphoresis, dyspnea, fever, flu-syndrome, hypertension, increased cough, lethargy, pain (unspecified), myalgia, pelvic pain, peripheral edema, pharyngitis, pruritus, rash (unspecified), and vasodilation. Infections including bronchitis, rhinitis, sinusitis, and urinary tract infections have been reported in 2—5% of patients receiving anastrozole.

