8.0. TOXICITY TO BE MONITORED AND DOSAGE MODIFICATION

8.1 Acute morbidity potentially associated with hormonal therapy will be monitored and recorded on the Therapy and Toxicity Summary Form (Form #xxxxx) for all patients during therapy. Any chronic toxicities will be recorded on the Follow-Up Form (Form #xxxxx) at each follow-up visit. This will include hot flashes (as defined in Section 10.5), vaginitis, vaginal bleeding, tumor flare, nausea, vomiting, constipation, diarrhea, abdominal pain, xerostomia. All toxicities will be assessed based on the NCI Common Toxicity Criteria. Others include wt gain, anxiety, confusion, dizziness, insomnia, paresthesia, thromboembolism, fatigue, UTI, arthralgia and injection site reaction.

Hot Flashes: Avoid hormone treatment for hot flashes. Use hormone alternatives, example; clonidine, Beralgan, prozac or effexor while continuing with treatment protocol treatment.

8.2 Unexpected or fatal toxicities (including suspected reactions) must be reported to the to the Study Coordinator

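### Section 15.4 ties the hospitalization criterion to unexpectedness, so an admission for a listed toxicity is not a serious adverse event on that criterion alone

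*Combined protocol and SAP*

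**What the plan says.** Section 15.4 gives several routes by which an adverse event becomes serious. One covers events that are "fatal or life-threatening (i.e., results in an immediate risk of death"; another covers permanent or substantial disability. The hospitalization route applies when the event "requires or prolongs hospitalization (only if related to an unexpected complication". The section closes with a catch-all: "This category also includes any other event the investigator judges to be serious or which would suggest a significant hazard, contraindication, side effect or precaution".

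Section 15.5 treats an event as unexpected when it is absent from what is "listed as a known toxicity of the investigational drug in the protocol, the consent form, the package insert, or the investigator brochure".

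Section 15.6 requires expedited reporting of events that are serious, unexpected and drug-related. After the instructions for that report comes a separate sentence: "If a non-serious AE becomes serious, this and other relevant follow-up information must also be provided to AstraZeneca and the FDA".

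Two sections of the protocol list the toxicity used as the example here. Section 3.0 (Toxicology) gives thromboembolism at 3.5% and adds: "Specific cases included angina, cerebrovascular accident, cerebral ischemia, cerebral infarct, myocardial infarction, myocardial ischemia, pulmonary embolism, retinal vein thrombosis, and thrombophlebitis". Section 8.1 names it again among the toxicities to monitor: "Others include wt gain, anxiety, confusion, dizziness, insomnia, paresthesia, thromboembolism, fatigue, UTI, arthralgia and injection site reaction".

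**The concern.** Seriousness describes the outcome of an event; expectedness describes whether the event was already known. Section 15.6 treats them as separate conditions. Section 15.4 does not: for hospitalization, and for no other route, it makes seriousness depend on expectedness.

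What is at stake is how admissions are classified in the period when they are most likely to be seen. Section 2.0 has definitive surgery follow treatment immediately, and 15.1 keeps the adverse event period open until 30 days after the last dose, so the surgical stay falls inside it. If a listed complication prolongs that stay, two investigators could classify the same event differently. A rule in 15.6 that depends on seriousness would then be applied differently too.

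**Working it through.** No arithmetic applies. The check is to follow one event through the rules: a woman on study is admitted, or kept in longer, with a non-fatal thrombophlebitis.

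1. **Is it listed?** Yes. Section 3.0 names it among the thromboembolic cases, and 8.1 names thromboembolism. Listing in any one of the four sources in 15.5 is enough, so the event is not unexpected.

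2. **Is it serious under 15.4?** Take each route in turn:

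| Route in 15.4 | Limited by expectedness? | Result for this event |
|---|---|---|
| Fatal or life-threatening | No | Not met unless there is immediate risk of death |
| Disabling | No | Not met unless disability is lasting or substantial |
| Hospitalization | Yes | Not met, because the event is listed |
| Closing catch-all | No | Depends on the investigator's judgment, or on whether the event suggests a significant hazard or side effect |

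3. **Is an expedited report due under 15.6?** No, because the event is listed. Removing the parenthesis from 15.4 would not change this.

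4. **Is a follow-up report due under 15.6?** The sentence sets no expectedness condition of its own; it asks only whether a non-serious event has become serious. Admission alone does not bring that about. Any of the other routes in step 2 would.

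5. **Does another rule fill the gap?** Section 8.2 sends unexpected or fatal toxicities to the Study Coordinator. A non-fatal listed event is neither. Section 8.1 does require the event to be recorded and graded by the NCI Common Toxicity Criteria.

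The same trace applies to other listed events in section 3.0 that could lead to admission, such as angina or urinary tract infection.

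**The case against.** The case on the other side has four parts.

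- **The parenthesis may mean something else.** Section 15.5 defines an unexpected event, while 15.4 speaks of a complication. With surgery following directly on treatment, the phrase may have been meant to set aside planned admissions. That is probably the intent, but the text does not say it. A planned operation is in any case hardly an untoward occurrence under 15.1. The ambiguity is itself a reason to change the wording.
- **Failing one route does not make an event non-serious.** This stands. A reader might infer that an admission for a listed toxicity is never serious and never triggers the follow-up report. The documents do not support that. Many of the listed thromboembolic forms, such as infarction, stroke or pulmonary embolism, could qualify as life-threatening or disabling. The second limb of the catch-all is also not tied to the investigator's judgment.
- **The follow-up sentence may belong only to the expedited stream.** It sits below the instructions for serious, unexpected, drug-related events. If it is confined to those, listed events fall outside it whatever 15.4 says. This reading is open, so the effect on follow-up reports is conditional.
- **The safety data are still collected.** This also stands. Section 8.1 records and grades toxicities for all patients, 15.1 captures adverse events regardless of cause, and section 11.0 gives the Study Committee responsibility for monitoring toxicity. Only the serious label is in question.

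**Conclusion.** The wording of 15.4 is wrong as it stands, with a limited consequence. If unexpected has its 15.5 meaning, an admission or prolonged stay for a listed, non-fatal toxicity is not serious by the hospitalization criterion alone. Its status then rests on another route, often on judgment. The same holds for the follow-up report, if that sentence reaches beyond the expedited stream.

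Two stronger inferences should be resisted. The first is that known risks will look milder than they were: section 11.0 specifies no analysis based on serious events, and the events remain on the toxicity forms with their grades. The second is that the 3.5% for thromboembolism, applied to the 42 planned patients, gives the number of missed serious events. That product would count any thromboembolism. The relevant subset is admitted, non-fatal, neither life-threatening nor disabling, and not caught by the catch-all, and the documents give no rate for it. The 3.5% is also quoted without an exposure time, whereas section 7.1 plans 2 to 4 weeks of treatment.

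The primary endpoint, the sample size and expedited reporting are untouched. This is a worthwhile correction to safety classification, not a critical flaw.

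**What to change.** In 15.4, replace the parenthesis after hospitalization with: *(other than the admission planned for the protocol lumpectomy or mastectomy)*. Leave expectedness to 15.5 and 15.6, where it decides only whether an event is expedited. Because the criterion would still cover prolonged stays, a complication that extends the planned surgical stay would count as serious whether or not it is listed.

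The cost is one phrase in the protocol and probably a few more events classed as serious. It adds no expedited FDA reports for listed events, and it keeps what was probably the purpose of the parenthesis.
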